2. Varenicline: Varenicline will be administered as clinically indicated and will begin approximately 4-6 weeks prior to surgery. All participants will receive a 1-week dose induction period (0.5mg QD Days 1-3, 0.5mg BID Days 4-7) before transitioning to a full maintenance dose (1mg BID). The target-quit date (TQD) will be on Day 8 (week 2) and will coincide with the 1st day of the maintenance dose, consistent with recommended guidelines. Participants will receive a 1-week supply of varenicline (with 3 days of extra doses in the event of an unpredicted event) in blister packs at each study visit. This will enable us to better track medication adherence and adverse events, and will help encourage participants to attend weekly visits. There is nothing experimental about the use of varenicline in this study. Participants will receive a 2-week supply of varenicline (with 3 days of extra doses) at the visit immediately prior to the participants’ scheduled surgery in order to allow participants to continue taking the full maintenance of varenicline uninterrupted, while also allowing for ample healing time before returning for the first study visit post-surgery.

3. Incentives: Incentive payments will begin on the TQD (week 2) and will be in place for 5 weeks or until surgery (whichever is sooner). Participants will receive monetary based incentives for biochemical evidence of smoking abstinence. Abstinence will be determined via breath carbon monoxide (CO) ratings during Week 2, and via urinary cotinine for the duration of the study. The transition from CO to cotinine is a common procedure that provides a method for awarding incentives to participants who have recently begun abstaining from smoking but will still test positive for cotinine (because of the long elimination half-life of cotinine). Cotinine-based testing will be used as the definition of abstinence during weeks 3-12. CO will be tested using mobile meters and abstinence will be

Table 2. Incentive and Compensation Structure

Study Week	Study Visit	Incentives	Visit Payments
Screening			\$30
1	-6		\$20
2	-5	\$20	\$20
3	-4	\$40	\$20
4	-3	\$60	\$20
5	-2	\$80	\$20
6	-1	\$100	\$20
7	1		\$50
8	2		\$60
9	3		\$70
10	4		\$80
11	5		\$90
12	6		\$100
Follow-up			\$50
Total:		\$300	\$650

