- b. Justification and safety information if FDA approved drugs will be administered for non-FDA approved indications or if doses or routes of administration or participant populations are changed.

N/A

- c. Justification and safety information if non-FDA approved drugs without an IND will be administered.

N/A

8. Study Statistics

Outcome Measures: We will collect a variety of outcome measures to enable a full characterization of decision-making factors at baseline, and the impact of this intervention on smoking status, postsurgical outcomes, opioid analgesia utilization, and cost.

- a. Primary outcome variable.

Smoking Outcomes: Our primary outcome variable will be smoking status. Smoking abstinence will be defined as a negative biochemical sample + self-report of no smoking for the past 7 days, mean % negative samples, and mean continuous negative samples. Smoking will be evaluated within each pre and post-surgical phase, and collapsed over the 11-week targeted cessation period (following the TQD during week 2). Point prevalence smoking abstinence at the follow-up will be defined as a negative cotinine sample + self-report of no smoking for the past 7-days.

b. Secondary outcome variables.

Secondary smoking outcomes will include ratings of nicotine withdrawal and craving, using standardized measures, and frequency of adverse events judged to be related to varenicline or smoking cessation.

Surgical Recovery Outcomes: A variety of postsurgical outcomes will be evaluated. These will include length of hospital stay, overall quantity and frequency of opioid analgesic use, pain ratings of during the recovery period, types and frequency of post-operative complications, frequency of admission into the intensive care unit, and 30-day hospital readmission rates.

c. Statistical plan including sample size justification and interim data analysis.

Since this is an open-label study design, results will be analyzed in a mostly descriptive method.

Smoking Outcomes: Smoking outcomes will be evaluated as a function of time over the 11-week intervention. Smoking cessation rates will also be compared from the pre to post-intervention phases.

Surgical Recovery Outcomes: Surgical outcomes will be evaluated as a function of percent biochemically-confirmed smoking abstinence, to assess whether the duration and/or magnitude of smoking abstinence is statistically associated with 30-day readmission rates, opioid analgesic use, and other surgical outcomes.

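### Does scoring the Week 2 visit hold a participant who quits on the Day 8 quit date to 80% presurgical abstinence?

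*Combined protocol and SAP*

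**What the plan says.** Section 8a gives the on-treatment definition as "Smoking abstinence will be defined as a negative biochemical sample + self-report of no smoking for the past 7 days", and lists beside it two sample-based summaries: the mean percentage of negative samples and mean continuous negative samples. It then says "Smoking will be evaluated within each pre and post-surgical phase, and collapsed over the 11-week targeted cessation period (following the TQD during week 2"). The follow-up definition is worded a little differently: "Point prevalence smoking abstinence at the follow-up will be defined as a negative cotinine sample + self-report of no smoking for the past 7-days".

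On timing, Section 5a (Varenicline) states "The target-quit date (TQD) will be on Day 8 (week 2) and will coincide with the 1st day of the maintenance dose". Section 5a (Incentives) states "Incentive payments will begin on the TQD (week 2) and will be in place for 5 weeks or until surgery (whichever is sooner"), and on the marker, "Abstinence will be determined via breath carbon monoxide (CO) ratings during Week 2, and via urinary cotinine for the duration of the study". The same section makes cotinine the definition of abstinence in weeks 3-12. It explains the CO step as a way to reward people who have just stopped but still carry cotinine. Under Biochemical Testing, urine cotinine is named as the primary outcome measure.

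Section 8c calls the analysis mostly descriptive. It adds "Smoking cessation rates will also be compared from the pre to post-intervention phases" and "Surgical outcomes will be evaluated as a function of percent biochemically-confirmed smoking abstinence".

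**The concern.** A 7-day look-back taken on the quit date covers days on which nobody had yet been asked to stop. The CO test removes the biochemical carry-over in Week 2, but Section 8a makes no matching exception for the self-report. The 11-week period matches a count of visits only if Week 2 is included, and the switch from a biochemical sample on treatment to a cotinine sample at follow-up could be read as leaving room for a scored CO result.

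If Week 2 were scored this way, the presurgical rate would be pulled down and the post-surgical rate would not. A relapse after the incentives end could then be hidden. Presurgical phases of 4 to 6 weeks would also give equally abstinent people different percentages, and Section 8c relates surgical outcomes to a percentage of abstinence. Smoking status is the primary outcome and is meant to inform a larger trial, so the question deserved a check.

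**Working it through.** **Inputs.** Quit date Day 8 (Section 5a, Varenicline). Testing for incentives starts on the quit date (Section 5a, Incentives). Table 2 has presurgical weeks 1-6 and post-surgical weeks 7-12. The presurgical phase is about 4-6 weeks (Section 5a). The composite is a negative sample plus 7 smoke-free days (Section 8a).

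**1. Reproducing the 11 weeks.** Two counts give the stated figure.
- Visits: weeks 2-12 = 5 presurgical + 6 post-surgical = 11.
- Elapsed time: Days 8-84 = 77 days, and 77/7 = 11.0 weeks, with 10 visits after Day 8 (weeks 3-12).

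So 11 weeks does not by itself show that a Day 8 sample is scored. The elapsed-time count assumes unbroken weekly visits. Section 5a resumes visits about two weeks after surgery, so the last visits may fall later; the visit fractions below do not depend on this.

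**2. Look-back.** The participant's last smoking day is Day 7.

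| Visit day | Days covered, visit day excluded | Days covered, visit day included | Result |
|---|---|---|---|
| 8 | 1-7 | 2-8 | fails both ways |
| 13 | 6-12 | 7-13 | fails both ways |
| 14 | 7-13 | 8-14 | passes only if visit day counts |
| 15 | 8-14 | 9-15 | passes both ways |

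**3. Individual ceiling if Week 2 is scored and the composite is averaged.** With six post-surgical visits assumed throughout:

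| Presurgical weeks | Presurgical | Overall |
|---|---|---|
| 6 | 4/5 = 80% | 10/11 = 91% |
| 5 | 3/4 = 75% | 9/10 = 90% |
| 4 | 2/3 = 67% | 8/9 = 89% |

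Scored from Week 3 on the six-week schedule: 4/4, 6/6 and 10/10. The mean percentage of negative samples has no stated self-report element and can reach 5/5 if CO is used in Week 2.

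**4. Size in a group.** Let p be the share who quit and stay quit, and f the share of those already smoke-free for the whole Week 2 look-back. The presurgical gap between the two scorings is p(1 − f)/5. As an assumption, take p = 0.6, the top of the short-term range quoted in the Background for incentives.
- f = 0: 0.6/5 = 12 points (12 × 0.8/20 = 48% against 12/20 = 60%).
- f = 0.5: 6 points (54% against 60%).
- f = 1: 0 points.

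With f = 0, the gap is 6 points at p = 0.3 and 20 points at p = 1. These are illustrations, not forecasts.

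**5. Are the conditions in the plan?**
- *Averaging the composite.* Section 8a attaches a mean only to the two sample measures. A composite read at the end of each phase has no ceiling.
- *Scoring Week 2.* Section 8a places the period after the quit date, and a Day 8 visit is on it. Section 5a names cotinine as the primary measure, uses it to define abstinence in weeks 3-12, and gives CO an incentive purpose.
- *Masked relapse.* This needs a pre- against post-surgical contrast. The comparison sentence in Section 8c speaks of pre- and post-intervention phases and does not settle that.
- *Distorted predictor.* This needs the biochemically confirmed percentage to be the presurgical composite. The closer match is the percentage of negative samples.

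**The case for a change.** The strongest case for a change is that the plan leaves open which visits are scored, the readings give different values for the primary outcome, and one sentence would close the gap without new visits or tests. Choosing the scoring after seeing the data is what prespecification is meant to prevent. Someone counting rows in Table 2 could arrive at weeks 2-12 in good faith. In the illustration with f = 0, if 2 of the 12 quitters smoke at every post-surgical visit, a fall from 60% to 50% (10/20) would appear as 48% to 50%.

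The omission is real and the arithmetic holds. The inference that the plan has a built-in 80% limit does not, because it rests on two rules the plan does not state and runs against Section 5a. The Day 8 fail is also a correct 7-day status, not a measurement error. The results are to be shown over time, so a Week 2 dip would be visible. Each visit collects both CO and urine, and the Time-Line Follow-Back is taken weekly, so either scoring can be produced. Follow-up point prevalence is unaffected.

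Nor is there one clearly better rule to write in. Dropping Week 2 leaves 2 scored presurgical samples instead of 3 in a 4-week phase. Scoring Week 2 on CO alone removes the ceiling and keeps the sample, but mixes two markers. Either choice is defensible.

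**Conclusion.** No change follows. The 80% ceiling (75% or 67% with shorter presurgical phases) is exact for one kind of participant: someone who smokes through Day 7, quits on Day 8, and has a Week 2 visit that is held on Days 8-13, scored on the 7-day composite and averaged with the later visits. The plan requires neither the scoring nor the averaging, and its own description of cotinine as the primary measure and as the definition for weeks 3-12 points to scoring from Week 3, where the ceiling disappears. The group effect ranges from 0 to 20 points on the six-visit schedule, depending on assumptions the documents do not fix, and it touches no hypothesis test, success threshold or stopping decision.

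This is a reporting detail that a competent analyst would fill: score abstinence by cotinine and self-report from Week 3, or show the Week 2 CO result separately, and say in the report which visits were counted. The conclusion assumes the data are collected as Section 5 describes and the analysis stays descriptive and single-arm, as Section 8c says.

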Screening: We are proposing to screen 40 individuals and complete 20 people for this initial study, which is consistent with other pilot/feasibility studies and will provide enough data to indicate whether a signal exists that would support further evaluation of this treatment approach in a larger-scale clinical trial study.

All participants will read and sign the informed consent with a trained staff member before conducting the screening visit, which will include self-report of smoking and other related variables, urinalysis verification of recent smoking, illicit drug, and pregnancy status, a medical history to determine medical eligibility, and completion of baseline decision-making measures. Participants will also provide written permission for study staff to access medical records to verify postsurgical outcomes and analgesic use, for study outcome measures.

Screening and Study-related Measures:

The following measures will be utilized during the study to determine eligibility and provide data necessary to complete the study aims. Individuals enrolled into the study will complete assessments weekly during treatment with one follow-up assessment 30 days after study completion. These data will be used to monitor changes in smoking status, mood or behavior changes related to medication or tobacco abstinence, health and pain-related outcomes, and vital signs.

- Time-Line Follow-Back (TLFB; Sobell et al., 1988): a validated self-report measure to record daily behaviors, including medication compliance and use of tobacco, alcohol, and other drugs/medications.

A past 30-day assessment will be conducted at baseline, with weekly assessments during the study

- Smoking History: brief self-report questionnaire of smoking history, quit attempts, use of pharmacotherapy, interest in quitting smoking, perceived ability to quit smoking and perceived health risk of smoking.
- Fagerström Test for Nicotine Dependence (FTND; Heatherton et al., 1991): 6-item self-report measure of nicotine dependence.
- Contemplation Ladder (Biener & Abrams, 1991): graphical description of process of change in relation to the need to quit smoking. Score ranges from 0 (no thoughts of quitting) to 10 (taking action to quit).
- Minnesota Nicotine Withdrawal Questionnaire-Revised (MNWQ-R; Hughes & Hatsukami, 1986): The 15- item self-report measure of nicotine withdrawal with good reliability and validity.

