- Questionnaire of Smoking Urges-Brief (QSU-B; Cox et al., 2001): 10-item self-report measure with good reliability and validity for detecting cigarettes craving.
- Medication Adherence Questionnaire (MAQ; Morisky et al., 1986): 4-item self-report measure used to identify potential problems with adherence to a medication regimen including quit smoking aid pharmacotherapies (Toll et al., 2007). Will be given monthly to monitor self-reported compliance with study medication.
- Beck Depression Inventory (BDI, Beck et al., 1961): 21-item self-report measure that evaluates symptoms of depression and suicidal thoughts. Scores are aggregated and categorized as minimal (0-13), mild (14- 19), moderate (20-28) or severe (29-63) depression. Participants who score >20, indicating moderate to severe depression, or who endorse >0 on the suicidal thoughts question (item 9) during screening will be excluded and referred to a clinician for further evaluation and referral if indicated. The BDI will be administered at every study visit to assess ongoing changes to mood.
- Columbia Suicide Severity Rating Scale (C-SSRS; Posner et al., 2003): The C-SSRS is a widely used suicide rating scale that is frequently used in clinical trials that administer varenicline. The C-SSRS will be used at baseline to assess lifetime history of suicidal events, and throughout the study.
- Weekly Update: We will administer a measure designed to assess changes in potential varenicline-mediated side effects over time at every weekly visit. This measure was designed in the context of large-scale trial to assess varenicline for alcohol treatment and was used successfully in a recently completed study to assess varenicline for smoking cessation (NA_00074143).
- Adverse Events Questionnaire: Locally developed measure to query potential side effects and concomitant medications. Specific questions address concerns with new onset of irritable and potentially violent behaviors.

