Study-related Measures: We will generate summary scores for each of the study measures and evaluate whether baseline values were positively associated with smoking outcome, and whether there were any changes in measures over time as a function of smoking status. These data will be used to help identify which measures may be most sensitive to change over time for a full-scale trial.

Sample Size Considerations: Our proposed sample of 20 completers is consistent with other open label studies of this kind. Additionally, our pilot data on bariatric patients from FY 2014 included only 23 smokers and still provided enough power to show a signal regarding the effects of smoking status on duration of hospital stay, total costs, and 30-day hospital readmissions. As such, we believe 20 completers will be a large enough sample to demonstrate an effect of the intensive intervention on promoting smoking cessation and minimizing post-surgical complications, and will also be a feasible sample size to recruit within the 2-year study period.

d. Early stopping rules.

This study will be stopped if we have evidence that enrolling participants into the study puts them at undue risk of experiencing complications during their surgery. We do not anticipate this happening, however since this is the first study of its kind in this population, we will monitor the data closely to verify safety of the participants.

9. Risks

a. Medical risks, listing all procedures, their major and minor risks and expected frequency.

Varenicline Administration:

Side-effect risks associated with varenicline administration (21): Allergic reactions to varenicline can be life-threatening and are generally characterized by a swelling of the face, mouth, and throat that can cause trouble breathing. *GI*: Nausea is the most frequent side-effect of varenicline and is present in approximately 30% of participants taking varenicline (versus 10% of participants taking placebo). The nausea associated with varenicline is generally transient, dose-dependent, of moderate intensity, and leads to dose discontinuation in only 3% (0.6% - 9%) of people who begin taking varenicline. Constipation, flatulence, and vomiting are more rare but possible side-effects. *Sleep complaints*: Insomnia (12% in

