Protection Against the Emergence of Neuropsychiatric Symptoms: The most worrisome potential side-effects of varenicline is the occurrence of rare neuropsychiatric symptoms (suicidal thoughts). Monitoring for such potential side effects will take place via multiple mechanisms. First, participants will be screened with specific questionnaires to history of suicidal thoughts and/or behaviors. Participants with severe prior or current psychiatric symptoms such as psychosis, suicidal behaviors, will be excluded from the study. Second, eligible participants will be informed of the risks for neuropsychiatric side effects and will be instructed to inform a study staff member immediately following any observed change in mood or worrisome thoughts, and will be assessed as clinically indicated. Third, trained staff members will meet with participants on a weekly basis to assess for adverse events using open-ended questions, as well as any emergency room visits and/or hospitalizations that may have occurred. Medical staff will be consulted if the participant endorses any behaviors or thought patterns that signify threats to patient safety or the safety of others, or any adverse event requiring medical attention including vital signs that are out of the norm. Adverse events will be reported to the IRB and the funding agency in accordance with reporting guidelines, and will be recorded as secondary outcome measures. Participants will complete a weekly assessment and the BDI at each study visit. Any endorsement of suicidal thoughts (at any level) on the BDI will prompt administration of the more comprehensive C-SSRS measure to fully characterize suicidal ideation. Any changes in weekly updates, regarding agitation, sadness, or hostility will also prompt assessment by a trained and qualified study investigator. A psychiatrist is always available to assist study staff in the evaluation and management of individual cases. In addition, the Emergency Department and Community Psychiatry department are located on the same campus as the BPRU smoking cessation clinic and are available to provide additional care to participants as needed. Following endorsement of any past 30 day suicidal ideations and/or behaviors, or if determined otherwise necessary by a trained member of the study staff, the individual will be escorted by a staff member to the Emergency Room (located across the street from the BPRU) for further evaluation and/or treatment. Participants will be reminded that they can stop

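### Section 8.b limits its adverse-event frequency to events judged related, while section 9.b sets no such limit; in an open-label single-arm study all events should be reported, with relatedness shown separately

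*Combined protocol and SAP*

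**What the plan says.** Section 8.b (Secondary outcome variables) places one adverse-event measure among the secondary smoking outcomes: the "frequency of adverse events judged to be related to varenicline or smoking cessation". Under Surgical Recovery Outcomes the same section also lists "types and frequency of post-operative complications, frequency of admission into the intensive care unit, and 30-day hospital readmission rates", with no condition on cause.

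Section 9.b (Protection Against the Emergence of Neuropsychiatric Symptoms) has trained staff ask about adverse events every week, in open-ended form, along with emergency visits and hospital stays. It says these events "will be recorded as secondary outcome measures". No relatedness condition is attached. That section also names suicidal thoughts as the most worrying possible effect of varenicline, and it provides that "Any endorsement of suicidal thoughts (at any level) on the BDI will prompt administration of the more comprehensive C-SSRS measure".

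Section 8.c (Statistical plan) has no paragraph on adverse events and names no safety population. Under Study-related Measures it plans summary scores, their baseline association with smoking outcome, and "whether there were any changes in measures over time as a function of smoking status". The BDI, given at every visit, falls under this. Section 5.a gives its bands, including "moderate (20-28) or severe (29-63) depression".

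**The concern.** Sections 8.b and 9.b are both current text, and they give different rules for the same secondary outcome. An analyst who follows 8.b would drop events judged unrelated. One who follows 9.b would keep them.

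The rule in 8.b depends on a causal judgement that this design supports poorly. Everyone receives varenicline, counselling and incentives, whoever makes the judgement knows this, and no control group shows the background rate. After surgery, low mood may come from pain, the operation, nicotine withdrawal or the drug, and these cannot be told apart reliably in a single patient. An event put down to pain or surgery would fall outside the 8.b frequency.

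Section 2 says that a positive signal would be used to support an application for a randomised trial. The planners of that trial would want to know how many treated patients had an event, as well as how many had one that staff attributed to treatment or to quitting.

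**Working it through.** **No plan figure to reproduce.** The documents give no expected event rate, no number dosed, and no alpha, power or effect size for the sample. The check is a comparison of text, with arithmetic only to show scale.

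**Step 1. The sections side by side.**

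| Place | What is counted | Limit by cause |
|---|---|---|
| 8.b, secondary smoking outcomes | Adverse-event frequency | Yes: varenicline or cessation |
| 8.b, surgical recovery outcomes | Complications, intensive care admission, readmission | None |
| 9.b, neuropsychiatric protection | Adverse events, asked about weekly | None |
| 8.c, study-related measures | Summary scores, including the BDI | Not applicable; no count of participants with an event |

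The events exposed to the 8.b limit are therefore the non-surgical ones judged unrelated. A mood or suicidality event attributed to pain or surgery is of this kind: the surgical outcomes do not pick it up, and a mean score can hide it.

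**Step 2. What the limit can do to the figure.** Let N be the number dosed, k the participants with a given event and r those whose event is judged related. The 8.b frequency is r/N, the unrestricted one is k/N, and the gap is (k − r)/N. N is assumed to lie between 20 (everyone dosed completes) and 40 (everyone screened is dosed, an extreme upper limit). For one participant left out:

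- N = 20: 1/20 = 5.0 percentage points
- N = 30: 1/30 = 3.3 points
- N = 40: 1/40 = 2.5 points

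At N = 20, a single event judged unrelated would be reported as 0/20 (exact 95% CI 0% to 16.8%) instead of 1/20 = 5.0% (0.1% to 24.9%).

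**Step 3. What an unrestricted count could and could not show.** With no events, the exact two-sided 95% upper limit is 1 − 0.025^(1/N). The chance of at least one case at true risk p is 1 − (1 − p)^N.

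| N (assumed) | Upper limit, 0 events | p = 1% | p = 5% |
|---|---|---|---|
| 20 | 16.8% | 18% | 64% |
| 30 | 11.6% | 26% | 79% |
| 40 | 8.8% | 33% | 87% |

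The values of p are illustrative; section 9.a says only that neuropsychiatric symptoms should be rare. The count describes what happened and cannot rule out a rare harm.

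**The case against.** The two sections can be reconciled. Section 8.b says the outcomes will include the related events, which need not be a complete list, and 9.b separately makes adverse events secondary outcomes. On that reading all events are already outcomes and 8.b highlights a subset. The limit is also broad: an event counts if it is attributed either to the drug or to stopping smoking, and suicidal thoughts in someone taking varenicline to quit would often qualify. Section 8.c summarises every study measure, and BDI scores are already banded. Estimating safety is not an objective in section 2, and 7.a describes varenicline here as ordinary clinical use. Protection in real time is in place under 9.b.

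Most of this stands, and it is why the point is minor. It does not settle which frequency will be reported, because 8.b is the section that defines the outcome and it carries a condition that 9.b lacks.

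Two stronger readings are tempting and are not supported:

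- **Safety will be tabulated in completers only, so that participants withdrawn for suicidality disappear.** The wording "Our proposed sample of 20 completers is consistent with other open label studies of this kind" stands under Sample Size Considerations, and "We are proposing to screen 40 individuals and complete 20 people for this initial study" stands under Screening. Both are targets for numbers, not analysis sets. Section 5.f removes participants from the study but does not say that their data are discarded. The denominator is unstated, which is different from a plan to exclude people.
- **The plan counts only related events.** The non-exhaustive wording in 8.b, the unrestricted statement in 9.b and the unrestricted surgical outcomes all speak against this.

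**Conclusion.** The concern holds as a minor inconsistency with a clear better choice. Section 8.b sets a relatedness condition that 9.b does not, and in this design that judgement is unblinded and has no comparator. The exposure is confined to non-surgical events judged unrelated.

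The size depends on two things the documents do not give: how many are dosed (20 to 40 assumed) and how many events are judged unrelated. Whether any would be is unknown.

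The lack of a participant count for suicidal thoughts or raised BDI is a lesser matter of detail, since 8.c already summarises these measures. Participant protection is not in question, and the smoking and feasibility conclusions do not change.

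**What to change.** **In 8.b**, replace the restricted outcome with the frequency of all adverse events among everyone who took at least one dose of varenicline, including participants later withdrawn. Show judged relatedness in a separate column. This agrees with 9.b and keeps the information that 8.b wanted.

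**In 8.c, as an optional descriptive line**, give n/N of dosed participants with:

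- any post-baseline BDI item 9 above 0, or any C-SSRS ideation or behaviour, stating how many had a post-baseline C-SSRS, because 9.b makes its use partly dependent on a trigger;
- a BDI total of 20 or more at any later visit, among those below 20 at baseline. The baseline condition is needed because screening excludes scores above 20, so a participant can enter with exactly 20.

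**Cost.** One changed phrase and, if wanted, one short table, from data already collected and with no new visits or procedures. The downside is that events due to surgery, pain or nicotine withdrawal are counted too and cannot be separated without a comparator. The intervals will be wide, and the text beside the table should say that a rare harm cannot be excluded.
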